The interaction between two factors (a and b) will be studied by estimating the Relative Excess Risk due to Interaction (RERI) (17) in order to identify departures from additivity [$RERI = RR_{\text{factors a and b}} - (RR_{\text{factor a}} + RR_{\text{factor b}} - 1)$]. A value of RERI = 0 indicates additivity of effects (no interaction), superadditivity (or synergism) if greater than 0, and subadditivity (or antagonism) if lower than 0. The interaction between the use of acid-suppressing drugs and clopidogrel will also be studied by stratification according to use of acid-suppressing drugs.

Exposure definition

The GPs record in the computer the name, dose, frequency, and number of pills prescribed. Exposure to study drugs will be categorized as: "current," when the supply of the most recent prescription lasted until index date or ended in the month before the index date; "recent," when it ended between one month and one year before the index date; "past," when it ended between one one and two years before the index date; and "non-use," when there was no recorded use in the two years before the index date. A secondary analysis will consider current when the supply of the most recent prescription lasted until index date or ended in the week before the index date.

Duration of use will correspond to the sum of days included in the time period of "consecutive" prescriptions: two prescriptions are considered "consecutive" when the time interval between the end of supply of the first

one and the beginning of supply of the second one is less than two months. We will categorize treatment duration into three groups: duration no greater than one month, duration between one month and one year, and duration greater than one year. Clopidogrel dose will be either 75 mg or 150 mg daily. Specific cutoff values for PPI dose (in mg) will be as follows: omeprazole 20, esomeprazole 40, lansoprazole 30, pantoprazole 40, rabeprazole 20, cimetidine 800, famotidine 40, nizatidine 300, ranitidine 300. Doses less than the cut-off value will be grouped under low doses, doses equal to the cut-off value under medium doses and doses greater than the cut-off value under high doses.

Power calculation

We expect to identify a cohort of patients discharged alive after an hospitalization for acute serious coronary heart disease in the vicinity of 25,000. This cohort will contribute an average of 4 years of follow-up resulting into 100,000 person-years. Assuming an annual incidence of 2% for MI/CHD death and 1% for UGIB, the expected number of cases will be 2,000 and 1,000 respectively. Accordingly, the number of exposed cases to clopidogrel would be 800 and 400 assuming a prevalence of clopidogrel use of 40%. If we assume that 40% of users of clopidogrel will be prescribed concomitantly PPI, these sample sizes will permit to detect a relative risk of 1.25 for MI/CHD and a relative risk of 0.75 for UGIB with a power greater than 80%, a 5% one-sided alpha error and a control/case ratio of 5.

Good Pharmacoepidemiology Practices

This study will be performed in accordance with the Guidelines for Good Pharmacoepidemiology Practices (2007) (18). The study protocol will have to be approved by an ethics review board: ISAC (Independent Scientific Advisory Committee) for the GPRD study and Multi-centre Research Ethics Committee (MREC) for the THIN study.

REFERENCES

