THIN covers about 5% of the UK population, and is age-, gender-, and geographically representative. Data from approximately 4 million patients are systematically recorded by participating general practitioners and sent anonymously to THIN. THIN collects and organizes this information in order to be used for research projects. The computerized information includes demographics, details from general practitioner's visits, diagnoses from specialist's referrals and hospital admissions, results of laboratory tests and a free text section. Prescriptions issued by the general practitioner are directly generated from the computer.

The READ classification is used to code specific diagnoses, and a drug dictionary based on data from the MULTILEX classification is used to code drugs in both databases.

Ascertainment of study cohort

Follow up will start on the first day after _____ once an individual meets the criteria of at least one year enrollment with the general practitioner, one year since first computerized prescription and being 50-84 years old. That date will be their start date¹. We will exclude patients with a recorded diagnosis of cancer before start date¹. We will also remove from the source population all persons aged 70 and above with a follow-up longer than one year and less than 2 health contacts during their total follow-up

(proxy for incomplete data recording). Follow-up will end on the first of the following:

1. The date of a qualifying event; which is a hospitalization for acute serious coronary heart disease: defined as acute myocardial infarction, revascularization of the coronary arteries, or unstable angina.
2. The attainment of age 85;
3. The date of recorded diagnosis of cancer;
4. The date of death;
- 5.

We will review computer profiles of all persons identified with a serious coronary heart disease (free text comments will not be requested at this stage) and will retain as our study cohort all patients with documented evidence of hospitalization for acute serious coronary heart disease and who are alive one month after the qualifying hospitalization (start date2).

AMI and CHD death: case ascertainment and validation

We will follow-up all study cohort members from start date2 until the earliest occurrence of one of the following endpoints:

1. The date of a code suggesting a hospitalization for acute myocardial infarction
2. The attainment of age 85;
3. The date of recorded diagnosis of cancer;
4. The date of death;
- 5.

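### Duration of use has no lower bound at the qualifying hospitalization, so the over-one-year class mixes patients already treated before that event with patients who stayed event-free on treatment after it

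*Protocol*

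**What the plan says.** All references are to the protocol.

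- **Exposure definition, duration.** "Duration of use will correspond to the sum of days included in the time period of" consecutive prescriptions. Two prescriptions belong to the same course when the interval between the end of supply of the first "one and the beginning of supply of the second one is less than two months". The classes are "duration no greater than one month, duration between one month and one year, and duration greater than one year".
- **Exposure definition, recency.** Current, recent, past and non-use are all set by distance back from the index date. Non-use applies "when there was no recorded use in the two years before the index date".
- **Ascertainment of study cohort.** Outcome follow-up begins for patients "who are alive one month after the qualifying hospitalization (start date2"). The diagnostic exclusion at the earlier entry point is cancer: "We will exclude patients with a recorded diagnosis of cancer before start date". Earlier use of clopidogrel or a PPI is not an exclusion here, nor in the section on UGIB case ascertainment. Entry requires "at least one year enrollment with the general practitioner" and one year since the first computerized prescription.
- **Statistical analysis.** Index dates may fall at any time from start date2. The main contrast is current use against non-use. The models adjust for follow-up time since start date2, coronary history and other covariates. Clopidogrel or PPI use before the qualifying event is not among them.
- **Study objectives.** A duration-response is an objective for clopidogrel and for aspirin/clopidogrel in each of the two parts, four times in all.

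**The concern.** The cohort is defined by a coronary event, and the time axis of interest starts just after it. A patient who was on clopidogrel when that event occurred, and who continued afterwards, carries the earlier months into the duration count. Such a patient had a coronary event despite treatment. A patient who started at the event and reached a year of use is someone who persisted and remained free of the study outcome. These are opposite kinds of selection, yet both end in the same duration class, in proportions that change with time since the event.

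At stake is the reading of the duration-response. A higher risk of AMI/CHD death in the longest class could reflect who is in it rather than how long the drug was taken. The argument is weaker for UGIB, where having had a coronary event on clopidogrel is not a failure of the same kind and total continuous exposure is a defensible measure.

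**Working it through.** **1. The plan's own figures.** 25,000 patients × 4 years = 100,000 person-years. At 2% and 1% a year this gives 2,000 and 1,000 cases; with 40% on clopidogrel, 800 and 400 exposed cases. Take PPI prevalence p0 = 0.40 among exposed controls and p1 = RR·p0/(1 − p0 + RR·p0) among exposed cases:

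- AMI/CHD death, RR 1.25: p1 = 0.50/1.10 = 0.4545.
- UGIB, RR 0.75: p1 = 0.30/0.90 = 0.3333.

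Power = Φ[(|p1 − p0| − 1.645·SE0)/SE1], with SE0 from the pooled and SE1 from the separate proportions, one-sided 5%. With five exposed controls per exposed case, power is 88.6% for AMI/CHD death and 80.9% for UGIB. With the 5,000 controls that are to be sampled (2.5 per case), the AMI/CHD figure is 84.0%. The stated power above 80% is reproduced.

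**2. When the over-one-year class can be reached.** Let the index date be m months after start date2, which is one month after the event. With supply counted up to the index date, a course that began at the event has lasted at most m + 1 months. Exceeding 12 months requires m > 11. Before that, the class is reachable only with pre-event supply.

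**3. How much follow-up this covers.** Mean follow-up is 48 months. Its distribution is not given, so two shapes are shown:

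- everyone followed for 48 months: 11/48 = 22.9%;
- exponential with mean 48 months: 1 − exp(−11/48) = 20.5%.

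These are shares of all person-time. They are not the share of over-one-year users who were treated before the event, which the protocol does not give.

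**4. Whether the covariates help.** Within those 11 months, comparing over one year with shorter use compares patients with pre-event supply with a group made up largely of other users. Follow-up time cannot separate them, because both occur at the same follow-up time. Coronary history may reduce the difference but does not record who was treated before the event.

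**5. Illustration for duration (assumed inputs).** If a share s of the over-one-year class are carried-over users with h times the event rate of the rest, a true relative risk of 1 appears as 1 + s(h − 1):

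| s | h = 1.25 | h = 1.5 | h = 2 |
|---|---|---|---|
| 10% | 1.025 | 1.05 | 1.10 |
| 20% | 1.05 | 1.10 | 1.20 |
| 30% | 1.075 | 1.15 | 1.30 |

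**6. Illustration for the PPI contrast (assumed inputs).** With shares a1 and a0 of carried-over users among clopidogrel users with and without a PPI, the bias factor is [1 + a1(h − 1)]/[1 + a0(h − 1)]. At h = 2:

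- 20% against 10%: 1.2/1.1 = 1.09;
- 30% against 10%: 1.3/1.1 = 1.18;
- equal shares: 1.00.

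**7. Power if carried-over users are set aside (assumed shares of exposed cases and controls).**

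| Set aside | AMI/CHD death, 5 per case | AMI/CHD death, 2.5 per case | UGIB, 5 per case |
|---|---|---|---|
| 5% | 87.2% | 82.3% | 79.1% |
| 10% | 85.6% | 80.5% | 77.1% |
| 20% | 81.8% | 76.4% | 72.7% |
| 30% | 77.2% | 71.4% | 67.6% |

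**The case against.** - **The protocol never says that it counts back through the event.** This is true; it follows from a definition with no lower bound. A start point for drug courses might also be left to an analysis plan. But the protocol itself fixes the duration variable and its classes, and followed literally they span the event.
- **The PPI contrast does not depend on the counting rule.** This stands. A reader might infer that unbounded counting creates a false clopidogrel–PPI interaction. That contrast concerns current users, and someone with supply at the index date is current wherever the count begins. Distortion would need pre-event clopidogrel use to differ by PPI co-use, and nothing in the protocol shows that it does.
- **Past use is not a problem for the main analysis.** This also stands. For index dates in the first 11 months, the past-use window lies wholly before the event, but past users are outside the comparison of current use with non-use, and no objective concerns them.
- **Restarting recency at the event would do harm.** This is correct. A patient whose supply ended shortly before the event would become a non-user, contaminating the reference group that the two-year lookback protects.
- **Not every carried-over user is a treatment failure.** Qualifying events include revascularization, and coronary history is in the model. Both points reduce the likely size; neither separates the groups.

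**Conclusion.** The point holds for the duration-response objectives, chiefly for AMI/CHD death. Under the rule as written, the over-one-year class consists only of patients with pre-event supply for the first 11 months after start date2, about 20.5% to 22.9% of follow-up. After that it mixes them with patients who persisted event-free. The planned covariates do not separate the two.

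That timing follows from the protocol's own dates and mean follow-up. The size and direction of the bias do not: the range of 1.03 to 1.30 rests on assumed shares and assumed excess risks, with no allowance for the planned adjustment. For the PPI contrast the conclusion is only that an effect is possible. The illustrative 1.09 to 1.18 matters beside the design relative risk of 1.25 if such an imbalance exists, but it is no evidence of one. The stated power calculation is unaffected.

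**What to change.** 1. Keep the recency classes defined from the index date, including the two-year lookback for non-use.
2. Count duration of clopidogrel and of PPI from the qualifying hospitalization, and say so in the Exposure definition.
3. Add use of each drug in the year before that hospitalization as a separate yes/no covariate. The entry rule guarantees one recorded year before start date1, and the qualifying event comes later, so this year exists for everyone.
4. Repeat the duration and PPI analyses in patients with no clopidogrel in that year, as a secondary analysis. Truncating duration alone would not deal with a PPI imbalance; items 3 and 4 address it.

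The cost is some extra derivation from data already held. Post-event duration will be more closely tied to follow-up time, which is already in the model, and the over-one-year class will be empty for the first 11 months. Over those months the pre-event year lies from m + 1 to m + 13 months before the index date, inside the two-year lookback. Non-users of clopidogrel then have no pre-event-year use by definition, so the clopidogrel covariate separates patients only among those with recorded use. The repeat analysis has fewer exposed subjects: UGIB power starts at 80.9% and is 79.1% once 5% are set aside, so it would probably fall below 80%. That is why the restriction should not be primary.
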